7.6 FURTHER ENDPOINTS

Time to event endpoints

Further time to event endpoints will generally be analysed in a Cox proportional hazards model similar to the primary analysis on RS. If the endpoint does not include any cause of death, a CIF plot with all-cause mortality as competing risk will be displayed; otherwise, a CIF plot with causes of death not included in the endpoint as competing risk will be displayed.

Continuous endpoints:

The following endpoints will be evaluated by mixed models repeated measures (MMRM) as defined in the protocol.

- HbA_{1c} change from baseline over time (OC-AD on the randomised set and OC-OT on the treated set)
- SBP, DBP change from baseline over time (OC-AD on the randomised set and OC-OT on the treated set)
- Weight change from baseline over time (OC-AD on the randomised set and OC-OT on the treated set)
- NT-pro BNP relative change from baseline over time (OC-AD on the randomised set and OC-OT on the treated set) (value will be transformed to the log scale before MMRM analysis. Estimates obtained from the model will then be back-transformed and reported on the original scale.)
- KCCQ overall summary score change from baseline at week 52 (OC-AD on the randomised set and OC-OT on the treated set) (model will include all timepoints up to week 52)
- KCCQ individual domains change from baseline at week 52 (OC-AD on the randomised set and OC-OT on the treated set) (model will include all timepoints up to week 52)
- KCCQ total symptom score change from baseline at week 52 (OC-AD on the randomised set and OC-OT on the treated set) (model will include all timepoints up to week 52)

- KCCQ based on patient-relevant outcome change from baseline at week 52 (OC-AD on the randomised set and OC-OT on the treated set) (model will include all timepoints up to week 52)
- UACR relative change from baseline over time (OC-AD on the randomised set and OC-OT on the treated set) (value will be transformed to the log scale before MMRM analysis. Estimates obtained from the model will then be back-transformed and reported on the original scale.)
- eGFR (CKD-EPI)_{cr} change from baseline over time (OC-AD on the randomised set and OC-OT on the treated set)

As outlined in the protocol, the above endpoints will be analysed in a mixed model with repeated measures (MMRM), including baseline value, age, LVEF and eGFR (CKD-EPI)_{cr} at baseline as linear covariates and treatment group, visit, visit by treatment interaction, baseline by visit interaction, geographical region, gender and baseline history of DM as fixed effects. An additional factor of “week reachable” for the parameter in question, which for each patient is the theoretically reachable planned measurement based on the time of randomisation will adjust for the different planned study times.

An unstructured covariance structure will be used to model the within-patient errors.

Descriptive statistics will be calculated for the value at visit and change from baseline based on OC-AD on the randomised set and OC-OT on the treated set.

Additionally subgroup analyses will be performed as follows:

HbA_{1c} change from baseline will be evaluated by status of diabetes (non-DM, pre-DM, DM).

UACR will be evaluated by UACR at baseline (<30 mg/g, ≥30mg/g to ≤300mg/g, >300 mg/g).

In order to evaluate the mean effect on eGFR after approximately 3 years, the above described MMRM models will be used in the following way: a mean effect of the timepoints week 124, 148 and 172 will be calculated. This will be done for the imputations of OC and OC-AD.

For MMRM subgroup analyses, the model will additionally include the term for subgroup and the interaction terms for subgroup by visit, subgroup by treatment and subgroup by treatment by visit in addition.

To support analysis of renal function, eGFR throughout the trial will be categorized according to the following CKD staging: All calculations for the staging of renal function will be based on the originally measured laboratory values and the upper limit of normals (ULNs) given by the laboratory, not on normalised values with BI standard reference ranges.

Table 7.6: 1 CKD staging

Stage	eGFR (mL/min/1.73m²)	Description	Label for displays	Additional labels#
1	≥90	Normal or high	≥90	≥90 (CKD 1)
2	60 to <90	Mildly decreased	60 to <90	60 to <90 (CKD 2)
3A	45 to <60	Mildly to moderately decreased	45 to <60	45 to <60 (CKD 3a)
3B	30 to <45	Moderately to severely decreased	30 to <45	30 to <45 (CKD 3b)
4	15 to <30	Severely decreased	15 to <30	15 to <30 (CKD 4)
5	<15	Kidney failure	<15	<15 (CKD 5)

A shift table from baseline to last value on treatment for eGFR (CKD-EPI)_{cr} will be provided.

A summary will also be created representing the number of patients per treatment group who experienced a doubling in creatinine on treatment compared to baseline that was out of the normal range.

In cases where urine albumin values are reported to be below the quantification limits (e.g. <3 mg/L) the albumin / creatinine ratio is determined as missing and will not be replaced by estimated values.

Transitions from baseline to last value on-treatment based on the following UACR categories: normal (<30mg/g), microalbuminuria (30-≤300 mg/g and macroalbuminuria (>300 mg/g) will be presented.

For an evaluation of follow-up after discontinuation of trial medication an additional summary of the NT-proBNP, FPG, eGFR, UACR, creatinine and the KCCQ endpoints as above will be produced. This summary will include descriptive statistics for baseline, actual values and change from baseline to last on-treatment value and follow-up, and change from last on-treatment assessment to follow-up. The TS-FU patient set will be the basis for this summary, but only those patients with a valid baseline, last value on treatment and follow-up value will be included in all displays. Analyses will be repeated for patients with at least 52 weeks of cumulative exposure. FPG analysis will also be conducted by DM status at baseline.

Analyses of change from baseline to LVOT and FU as outlined above will be additionally modelled, separately for LVOT and FU. An analysis of covariance (ANCOVA) model including treatment group, gender, geographical region and history of DM as fixed effect and baseline eGFR (CKD-EPI)_{cr} (continuous), age (continuous), LVEF (continuous) and baseline of the endpoint (if not already included) as linear covariates will be used.

Descriptive statistics will be presented also for creatinine for the value at visit and change from baseline based on OC-AD on the randomised set and OC-OT on the treated set.

Win ratio:

An unmatched win ratio considering adjudicated CV death and adjudicated HHF will be analysed based on unmatched pairs. All patients randomised to empagliflozin will be compared to all patients randomised to placebo. Only common follow-up time will be considered for the comparison. Patients on empagliflozin are considered to have “won” the comparison if either the other patient has died due to CV causes while the patient on empagliflozin was still alive, or if both patients did not die due to CV causes, then if the other patient had more occurrences of HHF. The number of comparisons won is noted as N_W . Patients on empagliflozin are considered to have “lost” the comparison if the empagliflozin patient died due to a CV cause while the patient on placebo was still alive, or if both patients did not die due to a CV cause, then if the patient on empagliflozin had more occurrences of HHF. The number of comparisons lost is noted as N_L . The win ratio is N_W / N_L .

The rules for winning and losing follow Rogers 2014 (8) and analysis of the unmatched win ratio will be conducted as described in Pocock 2012 (10).

Other types of further endpoints

For other types of endpoints e.g. change in NYHA class at week 52, HCRU and EQ5D, descriptive statistics will be provided.

For NYHA class a shift table will also be provided for changes from baseline over time and for change from baseline to EOT and FU.

Pharmacokinetic analysis

Descriptive statistics of trough concentrations of empagliflozin will be presented.

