Note: references to “means of questions actually answered” imply the following.

If there are n questions in a scale, and the subject must answer m to score the scale, but the subject answers only n-i, where n-i >= m, calculate the mean of those questions as

(sum of the responses to those n-i questions) / (n-i)

not

(sum of the responses to those n-i questions) / n

Patient-preferred outcome is derived from response to the question about which domain is the most difficult for the patient to cope with at baseline:

- Loss of functional abilities: Physical Limitation Score
- Symptoms due to your heart failure: Total Symptom Score
- Your concern about how to manage your heart failure: Self-Efficacy Score
- Suffering from depression, anxiety, emotional liability because you have heart failure: Quality of Life Score
- Adapting your life to heart failure: Social Limitation Score

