Chronic dialysis is regarded as chronic if the frequency of dialysis is twice or more per week for at least 90 days.

*An eGFR (CDK-EPI)_{cr} reduction is considered sustained, if it is determined by two or more consecutive post-baseline central laboratory measurements separated by at least 30 days (first to last of the consecutive eGFR values). If there is no additional measurement ≥ 30 days after the eGFR reduction is observed and the patient dies within 60 days of this measurement, then the eGFR reduction is also considered sustained

Continuous endpoints:

The following endpoints will be evaluated by mixed models repeated measures (MMRM) as defined in the protocol.

- HbA_{1c} change from baseline over time (OC-AD on the randomised set and OC-OT on the treated set)
- SBP, DBP change from baseline over time (OC-AD on the randomised set and OC-OT on the treated set)
- Weight change from baseline over time (OC-AD on the randomised set and OC-OT on the treated set)
- NT-pro BNP relative change from baseline over time (OC-AD on the randomised set and OC-OT on the treated set) (value will be transformed to the log scale before MMRM analysis. Estimates obtained from the model will then be back-transformed and reported on the original scale.)
- KCCQ overall summary score change from baseline at week 52 (OC-AD on the randomised set and OC-OT on the treated set) (model will include all timepoints up to week 52)
- KCCQ individual domains change from baseline at week 52 (OC-AD on the randomised set and OC-OT on the treated set) (model will include all timepoints up to week 52)

- KCCQ total symptom score change from baseline at week 52 (OC-AD on the randomised set and OC-OT on the treated set) (model will include all timepoints up to week 52)
- KCCQ based on patient-preferred outcome change from baseline at week 52 (OC-AD on the randomised set and OC-OT on the treated set) (model will include all timepoints up to week 52)
- UACR relative change from baseline over time (OC-AD on the randomised set and OC-OT on the treated set) (value will be transformed to the log scale before MMRM analysis. Estimates obtained from the model will then be back-transformed and reported on the original scale.)
- eGFR (CKD-EPI)_{cr} change from baseline over time (OC-AD on the randomised set and OC-OT on the treated set)

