As outlined in the protocol, the above endpoints will be analysed in a mixed model with repeated measures (MMRM), including age, LVEF and eGFR (CKD-EPI)_{cr} at baseline as linear covariates and visit by treatment interaction, baseline by visit interaction, geographical region, sex and status of diabetes at baseline as fixed effects. An additional factor of “week reachable” for the parameter in question, which for each patient is the theoretically reachable planned measurement based on the time of randomisation will adjust for the different planned study times.

An unstructured covariance structure will be used to model the within-patient errors.

Descriptive statistics will be calculated for the value at visit and change from baseline based on OC-AD on the randomised set and OC-OT on the treated set.

Additionally subgroup analyses will be performed as follows:

HbA_{1c} change from baseline will be evaluated by status of diabetes (non-DM, pre-DM, DM).

NTproBNP change from baseline will be evaluated by baseline atrial fibrillation/atrial flutter (as determined by baseline ECG).

UACR will be evaluated by UACR at baseline (<30 mg/g, ≥30mg/g to ≤300mg/g, >300 mg/g).

In order to evaluate the mean effect on eGFR after approximately 3 years, the above described MMRM models will be used in the following way: a mean effect of the timepoints week 124, 148 and 172 will be calculated. Of the three timepoints, only those with at least 5 patients with a measurement at that timepoint will be included in the average calculation. This will be done for the imputations of OC-OT and OC-AD.

For MMRM subgroup analyses, the interaction term treatment-by-visit will be replaced by a treatment-by-subgroup-by-visit interaction term.

To support analysis of renal function, eGFR throughout the trial will be categorized according to the following CKD staging: All calculations for the staging of renal function will be based

on the originally measured laboratory values, not on normalised values with BI standard reference ranges.

Table 7.6: 1 CKD staging

Stage	eGFR (mL/min/1.73m ²)	Description	Label for displays	Additional labels#
1	≥90	Normal or high	≥90	≥90 (CKD 1)
2	60 to <90	Mildly decreased	60 to <90	60 to <90 (CKD 2)
3A	45 to <60	Mildly to moderately decreased	45 to <60	45 to <60 (CKD 3a)
3B	30 to <45	Moderately to severely decreased	30 to <45	30 to <45 (CKD 3b)
4	15 to <30	Severely decreased	15 to <30	15 to <30 (CKD 4)
5	<15	Kidney failure	<15	<15 (CKD 5)

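### The patient-preferred KCCQ outcome pools five domain scores chosen at baseline, but its MMRM has no term for the chosen domain, so some precision may be lost

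*SAP*

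**What the plan says.** The document contains the 2017 SAP and its later revision. The 2017 Section 7.6 names the endpoint "KCCQ based on patient-relevant outcome change from baseline at week 52" and does not say how the outcome is built. The revised Section 7.6 names it "KCCQ based on patient-preferred outcome change from baseline at week 52", and the revised Section 5.4.1 gives the derivation: "Patient-preferred outcome is derived from response to the question about which domain is the most difficult for the patient to cope with at baseline". Each of five possible answers there maps to one KCCQ score: Physical Limitation, Total Symptom, Self-Efficacy, Quality of Life or Social Limitation. The point therefore rests on the revised text.

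Revised Section 7.6 fits one MMRM to all its continuous endpoints. The linear covariates are age, LVEF and baseline eGFR. The other terms are "visit by treatment interaction, baseline by visit interaction, geographical region, sex and status of diabetes at baseline as fixed effects", plus a factor for the week a patient could have reached. On covariance it says: "An unstructured covariance structure will be used to model the within-patient errors". The chosen domain appears neither as a main effect nor in an interaction. The 2017 model did not have it either: "visit by treatment interaction, baseline by visit interaction, geographical region, gender and baseline history of DM as fixed effects".

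The same list also includes "KCCQ individual domains change from baseline at week 52", so each domain is analysed separately as well.

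**The concern.** For this endpoint the chosen domain is a baseline variable that decides which score is the outcome. Section 5.4.1 shows that the five scores are built differently:

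- Self-Efficacy has 2 items and can be scored from one.
- Physical Limitation has 6 items and needs three.
- Total Symptom averages two subscores that use 7 items between them.
- Only Physical Limitation and Social Limitation have a response option that is coded as missing.
- Self-Efficacy asks about confidence and understanding, which is a different subject from symptoms or limitation.

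It is plausible that scores built this way differ in spontaneous change and in regression to the mean, the more so because each patient picks the domain that is hardest to cope with. Differences in mean change that remain after baseline adjustment would go into the residual. A single baseline slope would also fit some domains less well than others. What is at stake is the width of the confidence interval for one exploratory endpoint.

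**Working it through.** The SAP states no sample size, SD, effect or power for this endpoint, so there is no figure to reproduce. All inputs below are assumptions.

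**1. Formula.** Let vb be the between-domain variance of mean change given baseline, and s² the within-domain residual variance. Then

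SE without domain / SE with domain = √(1 + vb/s²).

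| Residual SD | Between-domain SD | Ratio | SE larger by |
|---|---|---|---|
| 25 | 2 | √(1 + 4/625) | 0.3% |
| 20 | 2 | √(1 + 4/400) | 0.5% |
| 20 | 5 | √(1 + 25/400) | 3.1% |
| 15 | 5 | √(1 + 25/225) | 5.4% |
| 15 | 8 (extreme) | √(1 + 64/225) | 13.3% |

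**2. Simulation with baseline already in the model.** This was a week-52 ANCOVA with n = 200,000, five equal domains, within-domain SD 20, a baseline to week-52 correlation of 0.5 or 0.7, and one pooled baseline slope. It was fitted with and without a domain factor.

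| SD of domain mean levels | Correlation | SD of domain mean changes | SE larger by |
|---|---|---|---|
| 0 | 0.5 | 0 | 0.0% |
| 0 | 0.5 | 4 | 2.6% |
| 5 | 0.7 | 2 | 1.4% |
| 10 | 0.5 | 0 | 3.3% |
| 10 | 0.5 | 4 | 5.2% |

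The last row was the largest of the 18 settings run. In effective sample size it is 1.052² − 1 = 11%. The treatment estimate was essentially the same with and without the factor.

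The fourth row shows the baseline term doing part of the work. Given baseline, the domain intercepts there have SD 10 × (1 − 0.5) = 5, and the residual variance is 400 × (1 − 0.25) = 300. The formula gives √(1 + 25/300) = 1.041, or 4.1%, against 3.3% simulated. The pooled slope absorbs the rest.

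**3. The optional slope term.** A second simulation assumed n = 4800, domain shares 35/25/10/15/15%, residual SD 19, baseline SD 22, slopes on baseline of 0.30 to 0.70, and domain mean changes spanning 6, 10 or 14 points.

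| Span | SE, no domain | SE, domain | SE, domain and slopes | Effective N gain, domain | Further gain, slopes |
|---|---|---|---|---|---|
| 6 | 0.555 | 0.550 | 0.549 | 1.8% | 0.4% |
| 10 | 0.566 | 0.552 | 0.549 | 5.1% | 1.1% |
| 14 | 0.583 | 0.554 | 0.549 | 10.7% | 1.8% |

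Each gain is (SE ratio)² − 1, computed from the SEs as printed. As a check on the full model, 2 × 19/√4800 = 0.548. The domain term lowers the SE by a factor of 1.009, 1.025 or 1.052, in line with step 2. The 95% half-width (1.96 × SE) goes from 1.088 to 1.078, from 1.109 to 1.082, and from 1.143 to 1.086, which is 0.01 to 0.06 points on a 0-100 scale.

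Revised Section 6.6.1 scores KCCQ as 0 after death. Where that imputation applies, it could add variance that domain does not explain and move the gain towards the low end.

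**The case against.** The best case for the plan is that the common MMRM is deliberate. Section 4 of the revised SAP says that model terms were aligned across the document, and Section 7.6 refers to the protocol for the model. All five scores run from 0 to 100, and the patient's own baseline score is already in the model. The domains are also analysed one by one. The endpoint is outside the three-step hierarchy of Section 7.4.1, and even the other secondary endpoints are declared exploratory. On this view an optional covariate is a matter of taste.

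Much of this stands. It limits the size and importance of the point, and it means that the loss is conditional. It does not remove the point. Alignment is no argument against a covariate that matters for one endpoint only, because only here does the outcome scale differ between patients. The separate domain analyses do not sharpen the pooled estimate.

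A reader might infer three stronger things that the documents do not support:

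- **That the domains are known to differ.** The SAP gives no domain means, SDs, slopes or choice frequencies. It shows only different content and item counts.
- **That the treatment effect is biased.** Chosen domain is a baseline factor in a randomised comparison, so leaving it out costs precision only.
- **That chance imbalance in the domain mix is a separate harm.** Under randomisation it is already reflected in the larger standard error.

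**Conclusion.** The omission is real in the current text: five scores are pooled by a baseline answer, and the model neither carries that answer nor lets the baseline slope depend on it. The comparison remains valid, and no confirmatory result is touched.

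The cost depends on differences between domains that remain after baseline adjustment. These are plausible but not shown. Over the assumed ranges the standard error is about 0% to 5% larger without the term, or roughly 0% to 11% in effective sample size. It reaches about 13% only with an extreme between-domain SD of 8 against a residual SD of 15, and it is zero if domains do not differ given baseline. This is a small improvement at almost no cost, not an error that must be corrected.

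**What to change.** In revised Section 7.6, for the patient-preferred KCCQ outcome only, add chosen domain by visit to the MMRM fixed effects, and tabulate the chosen domain by treatment arm. Baseline score by chosen domain by visit can be added as an option. Its further gain is small (0.4% to 1.8% of effective sample size in step 3), and the lowest of these figures is within rounding of the SEs.

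The cost is one sentence in the SAP. With five domains and three post-baseline KCCQ visits up to week 52 (weeks 12, 32 and 52 in Table 6.7: 1), each term adds 4 × 3 = 12 parameters. That is negligible against the roughly 5750 patients planned in Section 9.6. The model will then differ slightly from the other KCCQ models, which the text should say.

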9.3 DEFINITION OF DM AT BASELINE

Table 9.3: 1 DM at baseline

Diabetes status at baseline	Definition
T1DM	Patients who fulfil one of the following: 
- investigator-reported medical history of diabetes on the medical history page AND 
- type of diabetes is T1DM
T2DM	Patients who do not have T1DM but fulfil one of the following: 
- investigator-reported medical history of diabetes on the medical history page OR- any pre-treatment HbA1c value ≥ 6.5 OR- stratification via IRT in group of diabetes with either missing assessment of history of diabetes on the medical history page, or no pre-treatment measurement of HbA1c available and investigator reported 'no' for the medical history of diabetes

Table 9.3: 1 DM at baseline (cont.)

Diabetes status at baseline	Definition
Pre-DM	
Patient who fulfil one of the following:
 
- investigator reported ‘no’ for the medical history of diabetes on the medical history page AND no pre-treatment HbA1c ≥ 6.5 and a pre-treatment HbA1c value of ≥ 5.7 and < 6.5 
OR
 
- stratification via IRT in group of pre-diabetes with either
○ missing assessment of history of diabetes on the medical history page and no pre-treatment HbA1c ≥ 6.5 or○ no pre-treatment measurement of HbA1c and investigator reported ‘no’ for the medical history of diabetes 
OR
 
- missing assessment of history of diabetes on the medical history page AND all pre-treatment HbA1c < 6.5 and a pre-treatment HbA1c value of ≥ 5.7 and < 6.5 and stratification via IRT in group of no diabetes
Normal (excluding pre-DM)	Patients not meeting the criteria of DM or pre-DM

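### HbA1c by diabetes status is fitted in one MMRM with one shared covariance matrix; if residual spread is larger in diabetics, their interval is too narrow and the other two are too wide

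*SAP*

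**What the plan says.** The file holds two SAP versions, the 2017 final and the revision of 12 February 2021. The revision is the current text, and the point is the same in both.

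- **Covariance.** Section 7.6 of both versions says "An unstructured covariance structure will be used to model the within-patient errors". Neither mentions a matrix per subgroup, separate models per subgroup, or a robust variance.
- **Analysis by diabetes status.** For HbA1c, "change from baseline will be evaluated by status of diabetes (non-DM, pre-DM, DM").
- **Subgroup model, current version.** "For MMRM subgroup analyses, the interaction term treatment-by-visit will be replaced by a treatment-by-subgroup-by-visit interaction term".
- **Subgroup model, 2017 version.** "For MMRM subgroup analyses, the model will additionally include the term for subgroup and the interaction terms for subgroup by visit, subgroup by treatment", with the three-way term by visit as well.
- **Category definitions, current version.** In Table 9.3: 1 a patient counts as type 2 diabetic with a reported history of diabetes or with "any pre-treatment HbA1c value ≥ 6.5", and there is no upper limit. Pre-diabetes is mainly a pre-treatment HbA1c of at least 5.7 and below 6.5 with no reported history. Normal is the remainder. Randomisation-system strata fill in where history or HbA1c is missing.

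**The concern.** An unstructured matrix lets variances and correlations differ between visits. It does not let them differ between groups of patients. In both versions the subgroup enters the fixed effects only, so every subgroup standard error rests on a residual variance averaged over the three categories.

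That average suits all three only if their residual variances are equal. Here the subgroup is formed partly on the outcome: one category is a band 0.8 points wide at baseline, while another is open-ended and includes anyone with known diabetes. Equal residual spread is therefore unlikely.

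In a mixed population, HbA1c by diabetes status is the interpretable HbA1c result, and Section 6.4 calls the diabetic/non-diabetic split the most important subgroup analysis. If the spread is unequal, precision is overstated in one category and understated in the other two. A larger sample does not cure this, because the ratio of model SE to true SE does not depend on the sample size.

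**Working it through.** The SAP states no SD, SE or interval width for HbA1c, so there is no figure of its own to reproduce.

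**Inputs.** The sample size is about 5750 (Section 9.6). Assumed, because the SAP does not give them: 1:1 arms, complete data, the shares of diabetes/pre-diabetes/normal (D/P/N), and the residual SD of HbA1c change in each category.

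**Formulas.** With complete data, for category g:

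- pooled SD = sqrt(sum of share_g × SD_g²)
- ratio of model SE to true SE = pooled SD / SD_g
- actual coverage of the nominal 95% interval = 2Φ(1.96 × ratio) − 1

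Worked example for SDs 1.0/0.4/0.3 and shares 0.50/0.33/0.17: pooled SD = sqrt(0.50×1.00 + 0.33×0.16 + 0.17×0.09) = sqrt(0.5681) = 0.754. The ratios are 0.754/1.0 = 0.75, 0.754/0.4 = 1.88 and 0.754/0.3 = 2.51. Coverage in diabetics is 2Φ(1.96×0.754) − 1 = 86.0%.

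**Range of SDs, shares 50/33/17**

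| SD D/P/N | Pooled SD | Width relative to correct, D / P / N | Coverage in diabetics |
|---|---|---|---|
| 1.2/0.4/0.3 | 0.888 | 0.74 / 2.22 / 2.96 | 85.3% |
| 1.0/0.4/0.3 | 0.754 | 0.75 / 1.88 / 2.51 | 86.0% |
| 0.8/0.4/0.4 | 0.632 | 0.79 / 1.58 / 1.58 | 87.9% |
| 0.8/0.5/0.5 | 0.667 | 0.83 / 1.33 / 1.33 | 89.8% |
| 0.6/0.5/0.5 | 0.552 | 0.92 / 1.10 / 1.10 | 92.9% |
| 0.5/0.5/0.5 | 0.500 | 1.00 / 1.00 / 1.00 | 95.0% |

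**Range of shares, SDs 1.0/0.4/0.3.** As the diabetic share goes from 34% to 80%, the diabetic ratio goes from 0.65 to 0.91 (coverage 79.7% to 92.5%). The pre-diabetic ratio goes from 1.62 to 2.27 and the normal ratio from 2.17 to 3.03.

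**Simulation** (1000 trials, about 5750 patients, four visits, common baseline slope, shares 50/33/17, SDs 1.0/0.4/0.3)

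| Covariance | Mean SE D / P / N | Coverage D / P / N |
|---|---|---|
| One shared matrix | 0.0281 / 0.0346 / 0.0483 | 86.5% / 99.9% / 100% |
| Separate per category | 0.0373 / 0.0184 / 0.0192 | 95.3% / 95.2% / 94.7% |

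With all SDs equal to 0.5, the shared matrix gave 94.9%, 95.6% and 94.3%, which is nominal within simulation error.

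**Absolute size in the same scenario.** The 95% half-widths under the shared matrix are 1.96×0.0281 = 0.055, 1.96×0.0346 = 0.068 and 1.96×0.0483 = 0.095 HbA1c points. With separate matrices they are 0.073, 0.036 and 0.038.

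**The case against.** **Unequal variance is not established by the document.** Table 9.3: 1 limits pre-treatment HbA1c, not the residual of later change, and the model already adjusts for baseline by visit. This stands. The definitions make unequal residual spread likely but do not prove it or give its size, so the conclusion has to be conditional.

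**The SAP is silent rather than explicit.** A common matrix is the usual default, and nothing forbids a grouped one. That is true, but a programmer following the text would fit the common matrix.

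**The practical damage is small.** A reader might infer that the pre-diabetic and normal intervals become so wide that absence of an effect could not be shown. The documents do not support that. At about 5750 patients, even the inflated half-widths above stay below 0.1 HbA1c points. Under the same assumptions the error in the diabetic half-width is about 0.02 points (0.055 against 0.073).

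**It should not be stretched to other endpoints.** A reader might extend the point to fasting glucose, where the 2017 version says "FPG analysis will also be conducted by DM status at baseline" and the current text keeps this with three categories. The ANCOVA described contains no treatment-by-diabetes term, so it may well be run within each category. UACR and NT-proBNP are modelled on the log scale, and nothing in the SAP shows unequal variance there.

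**No decision rests on it.** HbA1c is outside the three-step hierarchy in Section 7.4.1. Even the other secondary endpoints, which rank above it, are declared exploratory. This stands and limits the priority.

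**Conclusion.** The point holds in conditional form. As written, Section 7.6 gives one covariance matrix for three categories that are formed partly on HbA1c. If residual spread is larger in diabetics, their interval under-covers and the other two over-cover.

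Over the assumed SDs at shares of 50/33/17, coverage in diabetics is about 93% down to 85%, and the other intervals are about 1.1 to 3 times too wide. With equal SDs nothing is distorted. The direction needs only the larger spread in diabetics. The size depends on SDs and shares that the SAP does not give, so no single figure should be quoted as fact.

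The primary and key secondary conclusions are unaffected. This is a correction to the error bars of an exploratory result.

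**What to change.** Add to Section 7.6: for HbA1c by diabetes status, the MMRM is fitted separately in each diabetes category, or with the unstructured covariance estimated separately per category (in SAS, REPEATED with TYPE=UN and GROUP set to diabetes status). If the grouped model does not converge, separate models are used.

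The cost is one sentence and one program option, plus two extra covariance matrices. Table 6.7: 1 lists eight post-baseline on-treatment visits through week 148. If HbA1c were measured at all of them (its schedule is not shown), one matrix has 8×9/2 = 36 parameters and three have 108. That should be affordable at this sample size, but sparse late visits could cause convergence problems; for eGFR, Section 7.6 already plans for time points with fewer than five patients. Separate models remove the need for a grouped fit but could meet the same sparseness within a category. If the variances prove equal, little precision is lost.
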